#### **Demographics**

- 12. Is male or female, 65 years to 85 years of age, inclusive, at the time of signing the informed consent.
- 13. A female participant is eligible to participate if she is not pregnant or breastfeeding, and at least one of the following conditions applies:
- Not a WOCBP

OR

- A WOCBP and:
  - Uses an acceptable contraceptive method, or be abstinent from heterosexual intercourse as their preferred and usual lifestyle (abstinent on a long-term and persistent basis), as described in Appendix 5 during the intervention period and for at least 14 days after the last dose of study intervention. The investigator should evaluate the potential for contraceptive method failure (ie, noncompliance, recently initiated) in relationship to the first dose of study intervention. Contraceptive use by women should be consistent with local regulations regarding the methods of contraception for those participating in clinical studies
  - Has a negative highly sensitive pregnancy test (serum or urine as required by local regulations) within 120 hours before the first dose of study intervention. (If a urine test cannot be confirmed as negative [eg, an ambiguous result], a serum pregnancy test is required. In such cases, the participant must be excluded from participation if the serum pregnancy result is positive.) Additional requirements for pregnancy testing during and after study intervention are in Section 8.3.5.
  - Medical history, menstrual history, and recent sexual activity has been reviewed by the investigator to decrease the risk for inclusion of a woman with an early undetected pregnancy.

#### **Informed Consent**

14. The participant (or legally acceptable representative) has provided documented informed consent/assent for the study. The participant may also provide consent/assent for FBR. However, the participant may participate in the study without participating in FBR.

#### **Additional Categories**

15. Willing to comply with the study restrictions (see Section 5.3 for a complete summary of study restrictions).

#### 5.2 Exclusion Criteria

The participant must be excluded from the study if the participant:

#### **Medical Conditions**

- 1. Has agitation/aggression or psychosis that is attributable to concomitant medications, environmental conditions, substance abuse, or an active medical or psychiatric condition.
- 2. Has a MHIS Score > 4 at Screening (i.e., evidence of vascular dementia).
- 3. Has a known history of stroke or evidence from prior MRI scan (if available) that is clinically important in the investigator's opinion.
- 4. Has evidence of a clinically relevant neurological disorder other than the disease being studied (i.e., probable AD) at Screening, including but not limited to: vascular dementia, parkinsonism, frontotemporal dementia, Huntington's disease, amyotrophic lateral sclerosis, multiple sclerosis, progressive supranuclear palsy, neurosyphilis, dementia with Lewy bodies, posterior cortical atrophy, logopenic primary progressive aphasia, other types of dementia, intellectual disability, hypoxic cerebral damage, cognitive impairment due to other disorders, or head trauma with loss of consciousness that led to persistent cognitive deficits.
- 5. Has a history of seizures or epilepsy within the last 5 years before Screening.
- 6. Has evidence of a clinically relevant or unstable psychiatric disorder, based on DSM-5 criteria, including schizophrenia, schizophrenia spectrum or other psychotic disorder, bipolar disorder, major depressive disorder, or delirium. Note: Major depressive disorder in remission is not exclusionary and mild, stable, treated depression is not exclusionary.
- 7. Is at imminent risk of self-harm, based on clinical interview or on the C-SSRS, or of harm to others in the opinion of the investigator. Participants must be excluded if they report suicidal ideation with intent, with or without a plan (i.e., suicidal ideation Item 4 or 5 on the C-SSRS) in the past 2 months or suicidal behavior in the past 6 months.
- 8. Has a history of alcoholism or drug dependency/abuse within the last 5 years before screening.

MK-8189-017-04 FINAL PROTOCOL

39

9. Has a history of cancer (malignancy).

Exceptions: (1) Adequately treated nonmelanomatous skin carcinoma or carcinoma in situ of the cervix or; (2) Other malignancies that have been successfully treated with appropriate follow up and therefore unlikely to recur for the duration of the study, in the opinion of the investigator and with agreement of the Sponsor (e.g., malignancies that have been successfully treated  $\geq 10$  years prior to the prestudy [screening] visit).

- 10. Has a family history of prolonged QTc syndrome.
- 11. Has an estimated eGFR  $\leq$  50 mL/min/1.73 m^2 based on the MDRD.

## **MDRD Equation:**

eGFR (mL/min/1.73 m^2) = 175 x (serum creatinine)-1.154 x (age)-0.203 x (0.742 [if female]) x (1.212 [if black or African American])

At the discretion of the investigator a measured CrCl, as determined by a 24-hour urine collection, may be used in place of, or in conjunction with, the estimate of the eGFR.

Participants who have an eGFR or measured CrCl of up to 10% below of either 50 mL/min (for CrCl) or 50 mL/min/ $1.73m^2$  (for eGFR) may be enrolled in the study at the discretion of the investigator.

- 12. Has a history of significant multiple and/or severe allergies (e.g., food, drug, latex allergy), or has had an anaphylactic reaction or significant intolerability (i.e., systemic allergic reaction) to prescription or nonprescription drugs or food.
- 13. Previously developed severe EPS following administration of any prescribed medication or study treatment. Severe EPS is defined as follows: Parkinsonism type symptoms persisting for ≥3 days, or induction of a tremor that interferes with daily living, dystonia persisting for > 24 hours, or objective restlessness consistent with akathisia.
- 14. Is positive for HBsAg, hepatitis C antibodies or HIV.
- 15. Had major surgery, donated or lost 1 unit of blood (approximately 500 mL) within 4 weeks prior to the prestudy (screening) visit.

#### **Prior/Concomitant Therapy**

16. Has received treatment with monoamine oxidase inhibitors or unable to refrain from the use of co-medication with a moderate or strong inhibiting or inducing effect on CYP3A or moderate to strong inducing effect on CYP2C9 (CYP2C9 inhibitors are permitted) beginning approximately 2 weeks or 5 half-lives, whichever is longer, prior to administration of the initial dose of trial drug and throughout the trial.

#### **Prior/Concurrent Clinical Study Experience**

17. Has participated in another investigational study within 4 weeks (or 5 half-lives, whichever is greater) prior to the prestudy (screening) visit. The window will be derived from the date of the last visit in the previous study.

#### **Diagnostic Assessments**

18. Has a QTc interval >450 msec.

#### **Other Exclusions**

- 19. Does not agree to follow the smoking restrictions as defined by the CRU.
- 20. Consumes greater than 3 glasses of alcoholic beverages (1 glass is approximately equivalent to: beer [354 mL/12 ounces], wine [118 mL/4 ounces], or distilled spirits [29.5 mL/1 ounce]) per day. Participants who consume 4 glasses of alcoholic beverages per day may be enrolled at the discretion of the investigator.
- 21. Consumes excessive amounts, defined as greater than 6 servings (1 serving is approximately equivalent to 120 mg of caffeine) of coffee, tea, cola, energy drinks, or other caffeinated beverages per day.
- 22. Is a regular user of cannabis, any illicit drugs or has a history of drug (including alcohol) abuse within approximately 3 years. Participants must have a negative UDS (with the exception of cannabis and/or prescribed medications permitted at the discretion of the PI and Sponsor) prior to randomization.
- 23. Presents any concern by the investigator regarding safe participation in the study or for any other reason the investigator considers the participant inappropriate for participation in the study.
- 24. Is or has an immediate family member (eg, spouse, parent/legal guardian, sibling, or child) who is investigational site or Sponsor staff directly involved with this study.

#### 5.3 Lifestyle Considerations

#### 5.3.1 Meals and Dietary Restrictions

#### 5.3.1.1 Diet Restrictions

Fasting requirements for laboratory safety evaluations are specified in Appendix 2.

Participants should fast overnight prior to all visits to the CRU including the screening and poststudy visits. Otherwise, participants will consume their usual diet except for grapefruit products (section 5.3.1.2). At CRU visits, participants may be given a light breakfast following study treatment administration.

MK-8189-017-04 FINAL PROTOCOL

41

## 5.3.1.2 Fruit Juice Restrictions

Participants should refrain from the consumption of more than 1 grapefruit or 1 glass (8 ounces) of grapefruit juice a day, throughout the entire study period. Otherwise, participants can consume their usual diet throughout the study period.

# 5.3.2 Caffeine, Alcohol, and Tobacco Restrictions

## 5.3.2.1 Caffeine Restrictions

Caffeinated beverages or xanthine-containing products will be limited to no more than 6 units per day (1 unit = 120 mg of caffeine).

# 5.3.2.2 Alcohol Restrictions

Participants will refrain from consumption of alcohol 24 hours before all CRU visits including the screening and poststudy visits. Alcohol consumption is limited to no more than approximately 3 alcoholic beverages or equivalent servings (1 serving is approximately equivalent to: beer [354 mL/12 ounces], wine [118 mL/4 ounces], or distilled spirits [29.5 mL/1 ounce]) per day.

# 5.3.2.3 Tobacco Restrictions

Participants will follow the smoking restrictions (and if applicable, the use of nicotine/nicotine-containing products) defined by the CRU during visits.

## 5.3.3 Activity Restrictions

Participants will avoid unaccustomed strenuous physical activity (i.e., weightlifting, running, bicycling, etc.) from the screening visit until administration of the initial dose of study intervention, throughout the study and until the poststudy visit.

## 5.4 Screen Failures

Screen failures are defined as participants who consent to participate in the clinical study but are not subsequently randomized in the study. A minimal set of screen-failure information may be included, as outlined in the eCRF entry guidelines. Minimal information may include demography, screen-failure details, eligibility criteria, and any AEs or SAEs meeting reporting requirements.

## 5.5 Participant Replacement Strategy

If a participant discontinues from study intervention OR withdraws from the study a replacement participant may be enrolled if deemed appropriate by the investigator and Sponsor. The replacement participant will generally receive the same intervention or intervention sequence (as appropriate) as the participant being replaced. The replacement participant will be assigned a unique treatment/randomization number.

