# 4.2 Scientific Rationale for Study Design

MK-8189 will be evaluated for the treatment of neuropsychiatric symptoms in dementia. Prior to the conduct of a larger POC study, this smaller study (n=28, randomized such that 21 are on MK-8189 and 7 on placebo) will be conducted as an initial assessment of safety and tolerability in a similar patient population.

This will be a randomized, placebo-controlled study to ensure an objective assessment of safety and tolerability. An outpatient trial is preferred as changing the environment in this patient population may adversely affect cognitive status. However, if deemed appropriate by the investigator, a participant may be domiciled as described in Section 8.1.12. An ongoing trial has evaluated MK-8189 doses titrated up to 24 mg over 10 to 13 days in 21 healthy elderly participants and preliminary blinded data suggest MK-8189 is generally well tolerated, supporting outpatient dosing (refer to Section 2.2). However, as the tolerability may differ in a population with AD, the study will first enroll only 8 participants to ensure tolerability of the selected treatment regimen. If tolerability issues are found, a more conservative regimen will be administered to the remaining participants. At any time during treatment, the investigator may choose to down-dose a participant. The assessment of MK-8189 safety and tolerability from this trial, in which participants with AD with or without agitation-aggression and/or psychosis will receive study treatment for one month, will be used to determine if longer term safety and efficacy trials can be supported. Daily telephone calls by study staff to the participant, weekly safety evaluations and the requirement for participants to have a trial partner/caregiver will help ensure participant safety and compliance with study intervention administration and protocol requirements throughout the study.

As efficacy will not be assessed in this study, participants without or with neuropsychiatric symptoms (agitation-aggression or psychosis) will be permitted in the study. Those who are currently taking antipsychotics to control neuropsychiatric symptoms may be enrolled if it is clinically appropriate to have participants wash off their medication (e.g., participant is not tolerating current treatment or is not likely receiving benefit from the treatment). This will

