#### **6 STUDY INTERVENTION**

Study intervention is defined as any investigational intervention(s), marketed product(s), placebo, or medical device(s) intended to be administered to a study participant according to the study protocol.

Clinical supplies (MK-8189/placebo) will be packaged to support enrollment and replacement participants as required. When a replacement participant is required, the Sponsor or designee needs to be contacted before dosing the replacement participant. Clinical supplies will be affixed with a clinical label in accordance with regulatory requirements.

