## 6.3.2 Stratification

Intervention allocation/randomization will be stratified according to the following factors:

1. participants with and without agitation-aggression and/or psychosis symptoms

For example, participants without agitation-aggression and/or psychosis symptoms will be assigned starting at the low allocation range and participants with agitationaggression and/or psychosis symptoms will be assigned starting at the upper allocation range. For this protocol agitation-aggression and/or psychosis symptoms are defined as a severity score of  $\geq 1$  and frequency score of  $\geq 2$  on the NPI Agitation-Aggression and/or Delusions and/or Hallucinations domains.

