# 7 DISCONTINUATION OF STUDY INTERVENTION AND PARTICIPANT WITHDRAWAL

## 7.1 Discontinuation of Study Intervention

Discontinuation of study intervention does not represent withdrawal from the study.As certain data on clinical events beyond study intervention discontinuation may be important to the study, they must be collected through the participant's last scheduled follow-up, even if the participant has discontinued study intervention. Therefore, all participants who discontinue study intervention before completion of the protocol-specified treatment regimen

will still continue to participate in the study as specified in Section 1.3 and Section 8.1.9, or per a PCL, if available.

Participants may discontinue study intervention at any time for any reason or be discontinued from the study intervention at the discretion of the investigator should any untoward effect occur. In addition, a participant may be discontinued from study intervention by the investigator or the Sponsor if study intervention is inappropriate, the study plan is violated, or for administrative and/or other safety reasons. Specific details regarding procedures to be performed at study intervention discontinuation are provided in Section 8.1.9.

A participant must be discontinued from study intervention, but continue to be monitored in the study, for any of the following reasons:

- The participant or participant's legally acceptable representative requests to discontinue study intervention.
- The participant's treatment assignment has been unblinded by the investigator, or through the emergency unblinding call center.
- The participant interrupts study intervention administration for more than 2 consecutive days or has 4 cumulative missed doses.
- The participant has a medical condition or personal circumstance which, in the opinion of the investigator and/or Sponsor, placed the participant at unnecessary risk from continued administration of study intervention.
- The participant has a positive UDS except for allowed concomitant medication administered during trial, at any time during the study. The drug screen can be confirmed by a recheck at the discretion of the investigator after discussion with the Sponsor.
- Any participant with EPS requiring treatment that is not or cannot be managed by down dosing.
- The participant no longer has a trial partner/caregiver or the trial partner/caregiver withdraws consent and a substitute cannot be identified.

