#### 8.1.7 Assignment of Treatment/Randomization Number

All eligible participants will be randomly allocated and will receive a treatment/randomization number. The treatment/randomization number identifies the participant for all procedures occurring after treatment allocation/randomization. Once a treatment/randomization number is assigned to a participant, it can never be reassigned to another participant.

A single participant cannot be assigned more than 1 treatment/randomization number.

Refer to the study operations manual for detailed procedures for requesting a treatment/randomization number.

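### Section 5.5's same-intervention default lets a site predict a replacement's assignment before the first dose when it has seen the replaced participant's emergency code

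*Combined protocol and SAP*

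**What the plan says.** Replacement is optional. Under Section 5.5, after a discontinuation or withdrawal, "a replacement participant may be enrolled if deemed appropriate by the investigator and Sponsor". The default for the assignment is: "The replacement participant will generally receive the same intervention or intervention sequence (as appropriate) as the participant being replaced". The replacement gets a new number: "The replacement participant will be assigned a unique treatment/randomization number". Section 6 adds a Sponsor step: "When a replacement participant is required, the Sponsor or designee needs to be contacted before dosing the replacement participant".

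Section 7.1 lists the reasons that oblige a participant to stop study intervention while staying under observation. One of them is: "The participant's treatment assignment has been unblinded by the investigator, or through the emergency unblinding call center". Section 8.1.10 repeats the obligation and adds that, after an emergency unblinding, the investigator, site staff and Sponsor staff may hold the code.

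On allocation, Section 8.1.7 states: "All eligible participants will be randomly allocated and will receive a treatment/randomization number". Section 6.3.1 assigns participants at random from a computer-generated list, and Section 6.3.2 stratifies that list by the presence of agitation-aggression or psychosis symptoms. Section 6.3.3 says investigators and others involved in dosing or clinical evaluation do not know the assignments. None of these sections makes an exception for replacements.

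**The concern.** Random allocation protects a trial only if the people who enrol and assess a participant cannot foresee the assignment. A rule that copies the assignment of the person replaced passes on whatever the site knows about that person. In most cases the site knows nothing certain. After an emergency unblinding it may know the code, and the same event obliges that person to stop, which opens the way to replacement.

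The primary endpoints are adverse events and adverse events leading to discontinuation. Investigators judge intensity and causality. Section 4.2.2 justifies the placebo control by the need for objective assessment of adverse events. An investigator who knows what a replacement is taking cannot give that kind of assessment for that participant.

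**Working it through.** **1. The plan's own figure.** Section 4.2 gives the sample as "n=28, randomized such that 21 are on MK-8189 and 7 on placebo". 21 + 7 = 28, so the stated total is reproduced. 21/28 = 0.75 and 7/28 = 0.25. Under fresh randomization, the chance that a new participant is on active is 75% and on placebo 25%. Section 9.9 gives no power calculation, so there is no further figure to reproduce.

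**2. The chain of rules.**
- Code broken → study intervention must stop (7.1, 8.1.10).
- Study intervention stopped → replacement possible, with the investigator sharing the decision (5.5).
- Replacement enrolled → by default, same intervention as the person replaced (5.5).
- Replacement identified as such before dosing, because the Sponsor must be contacted (Section 6).
- Investigator and site staff may hold the code of the person replaced (8.1.10).

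No section of the protocol provided for review excludes an unblinded participant from same-intervention replacement, requires the replacement to enrol at another site, or keeps the site from knowing who is being replaced.

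**3. How predictable the assignment becomes.** Section 5.5 says *generally*, so the default can have exceptions. Let g be the share of replacements that follow it, and assume the rest are drawn afresh at 3:1. The documents give no value for g, so the intermediate values below are assumptions.

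- Replaced participant on active: P(replacement on active) = g + (1 − g) × 0.75
- Replaced participant on placebo: P(replacement on placebo) = g + (1 − g) × 0.25

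| g | Replaced on active | Replaced on placebo |
|---|---|---|
| 0 (fresh randomization) | 0.75 | 0.25 |
| 0.80 | 0.80 + 0.20 × 0.75 = 0.950 | 0.80 + 0.20 × 0.25 = 0.850 |
| 0.90 | 0.90 + 0.10 × 0.75 = 0.975 | 0.90 + 0.10 × 0.25 = 0.925 |
| 0.95 | 0.95 + 0.05 × 0.75 = 0.9875 | 0.95 + 0.05 × 0.25 = 0.9625 |
| 1 (default always applied) | 1 | 1 |

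The gain in knowledge is largest for placebo: from 25% to at least 85% over the assumed range.

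**4. Side by side with the allocation text.** Section 8.1.7 speaks of all eligible participants being allocated at random. A replacement who inherits an assignment is eligible but is not allocated that way. Section 6.3.3 says the investigator is unaware of assignments. An investigator who has seen the code and enrols a same-intervention replacement is not unaware. These statements cannot all hold in this case.

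**The case against.** The best defence is that several conditions must coincide. Unblinding is reserved for the participant's welfare. A replacement is only a possibility. Site staff may, but need not, learn the code. The default is qualified. The study is multisite, and nothing says the replacement enrols at the same site or that the site is told whom it replaces. The Sponsor is contacted before dosing and could depart from the default. The procedure for requesting numbers is in an operations manual that is not part of these documents. All of this stands. It makes the case uncommon, but it does not close it, because no written rule tells the Sponsor to depart from the default.

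Same-arm replacement also has a purpose: it keeps the 21:7 split. If every replacement were drawn afresh, two lost placebo participants would bring back an expected 2 × 0.25 = 0.5 placebo participants. That is a fair reason not to abolish the default altogether.

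A reader might also infer three stronger things that the documents do not support.
- *That the site can guess the assignment after any adverse-event stop.* With r as the ratio of stopping rates, active to placebo, P(active | stopped) = 3r/(3r + 1). This is 75% at r = 1, which adds nothing to the 3:1 prior. It is 86% at r = 2 and 92% at r = 4. The documents give no rates by arm for this population, so no value of r can be defended.
- *That a sizeable part of the placebo arm would be affected.* No number of replacements is stated, and enrolling up to about 28 to obtain at least 16 completers already leaves room for about 28 − 16 = 12 non-completers.
- *That stratification is lost.* Section 6.3.2 says "Intervention allocation/randomization will be stratified according to the following factors" and exempts no one. Silence in 5.5 does not show that the strata are ignored.

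**Conclusion.** The point holds in a narrow form. Where the site has seen the code of the person replaced and the replacement enrols at that site, the replacement's assignment is foreseeable before the first dose. It is certain if the default is applied, and about 85% to 99% if 5% to 20% of replacements depart from it (assumed), against 75% active or 25% placebo under the planned ratio. Section 5.5 therefore has to be reconciled with Sections 6.3.1, 6.3.3 and 8.1.7.

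The text does not support saying that replacements' assignments are known in general. Certainty requires an unblinding that the site has seen, a decision to replace, enrolment at that site and the default being followed.

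The consequence is limited to possible expectation bias in the adverse event ascertainment and causality rating of the affected replacement. The analysis is descriptive, so no error rate changes. A replaced participant who received at least one dose stays in the All Participants as Treated population, so replacement removes no safety data. This is a cheap improvement to the wording rather than a flaw in the study's main result.

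**What to change.** Add to Section 5.5: the same-intervention default does not apply when the site knows the assignment of the participant being replaced; such a replacement is assigned the next unused randomization number in his or her own symptom stratum. Cross-reference this in Section 8.1.7, and state there that same-intervention replacement remains the exception to fresh allocation for other discontinuations. The Sponsor contact that Section 6 already requires before a replacement is dosed is the natural point to confirm which rule applies.

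The cost is protocol wording, plus a check that the allocation schedule and packaged supplies hold spare numbers in each stratum, which the documents do not state. The ratio may drift slightly. Counting each replacement in place of the person replaced, one placebo participant replaced by an active one turns 21:7 into 22:6, and the reverse gives 20:8. In a descriptive study that is a small price for keeping the assessor blind.
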